Full title:

A Prospective Randomised Control Trial Comparing Functional with Mechanical Axis Alignment in Total Knee Arthroplasty.

Short title:

RCT: FA TKA vs MA TKA

Chief Investigator:

[name] M.B.,B.S., F.R.A.C.S.(Orth), F.A.Orth.A.
Consultant Orthopaedic Surgeon St John of God Subiaco Hospital
Orthopaedic Surgeon Perth Hip and Knee Clinic

An Investigator Initiated Study

Protocol version number and date:

Protocol Version 1.6.1, 14/10/2021

STUDY SUMMARY

Identifiers	
ANZCTR Registry Number	ACTRN12621000060842
HREC St. John of God Subiaco Number	
Full (Scientific) title	A prospective randomised controlled trial comparing Functional with Mechanical Axis Alignment in total knee arthroplasty.
Health condition(s) or problem(s) studied	Knee osteoarthritis
Study Type i.e. Cohort etc.	Prospective, randomised, blinded, single-centre study
Target sample size	100
Location	St John of God Subiaco Hospital [name]
Study timelines	
Study Duration/length	4 years
Expected Start Date	01/12/2020
End of Study Date	01/12/2024
Key Study milestones	12/07/2020 - HREC applications 02/2021 - HREC meeting and ethical approval to commence study 03/2021- Commence patient recruitment and record outcomes of interest 12/2021 - Complete patient recruitment 12/2023 - Complete recording 2 yr outcomes of interest on all patients 06/2024 - Collate data and perform statistical analyses 02/2025 - Disseminate findings with publication in peer reviewed journal
Funding	Investigator initiated study
Sponsor	St John of God Healthcare
Chief Investigator	[name] [name] Email: [contact]
Co-Investigators	[name] [name] Email: [contact]
Principal Investigator/Study student	[name] [name] Email: [contact]

KEY WORDS

Functional Alignment
Kinematic Alignment
Mechanical Alignment
Total Knee Arthroplasty
Clinical Outcomes

LIST OF ABBREVIATIONS

AE	Adverse Event
AOANJRR	Australian Orthopaedic Association National joint Registry
AP	Anteroposterior
CI	Chief Investigator
CRF	Case Report Form
EQ5D-5L	European Quality of Life Measurement – 5 Dimension
FA	Functional Alignment
FJS	Forgotten Joint Score
HKA	Hip Knee Angle
HREC	Human Research Ethics Committee
KA	Kinematic Alignment
kFA	Kinematic axis alignment planned Functional Alignment
KOOS JR	Knee osteoarthritis outcome score. Junior version
LAT	Lateral
MA	Mechanical alignment
mFA	Mechanical axis alignment planned Functional Alignment
OA	Osteoarthritis
OKS	Oxford Knee Score
PHK	Perth Hip & Knee Clinic
PICF	Patient Information and Consent Form
PROMS	Patient Reported Outcome Measures
QA	Quality Assurance
RATKA	Robotically Assisted Total Knee Arthroplasty
RCT	Randomised Control Trial
RP	Research Physiotherapist
SAE	Serious Adverse Event
TKA	Total Knee Arthroplasty

CONTENTS

19.6 FUNCTIONAL TESTING PROTOCOLS

19.7 PATIENT INFORMATION FORM AND CONSENT

19.8 INTRAOP DATA COLLECTION FORM

19.9 DETAILED SURGICAL PLANNING

1. Introduction

Total knee arthroplasty (TKA) is the most effective treatment for patients with symptomatic end-stage knee osteoarthritis that has not responded to appropriate non-operative management. The aims of TKA are to provide pain relief and improve function. Accuracy of limb alignment, implant positioning, and soft tissue balance after TKA are important prognostic factors that affect postoperative clinical outcomes and long-term implant survivorship. Published literature has shown between 80% and 90% of patients are satisfied following this procedure. (1,2)

To this end there are two much debated theories of postoperative alignment after TKA. In total knee arthroplasty with mechanical alignment the aim is to achieve neutral limb alignment. This was to optimise longevity of TKA and prevent early failure. Total knee arthroplasty with kinematic alignment aims to restore the patient's own pre-arthritic knee anatomy with more natural alignment and preservation of native function. Enthusiasts debate both theories and it is yet to be established whether one is superior to the other.

An issue with both of these alignment theories is that they are purely related to bony anatomy. Neither considers soft tissue tension or balance before the bony cuts are made. Once the bony cuts are made the soft tissue balance is assessed and ligaments released until the TKA is balanced to the surgeon's satisfaction. In an initial cohort study well over 50% of patients in both groups required soft tissue releases to balance the TKA if these alignment theories were strictly adhered to.

The accuracy of soft tissue balancing is surgeon dependent and there is evidence that even experienced knee surgeons are poor at manually determining if a knee is balanced (3). This becomes particularly important when considering over half of these procedures throughout the world are performed by surgeons who undertake less than 25 TKA per year.

Robotic assisted TKA with the Mako robot (Stryker, Florida, USA) has enabled a pre-resection balancing technique. This enables assessment of soft tissue laxity and adjustment of the initial plan to achieve balanced soft tissue with alteration of component alignment. Once the knee has been virtually balanced on the planning software, robotic arm assisted surgery is undertaken to accurately replicate the plan resulting in a balanced TKA.

Functional alignment depends on the soft tissue tension to determine the TKA alignment and thereby minimizes the need for soft tissue release. As the collateral ligaments due not contract through the disease process of osteoarthritis, re-tensioning these ligaments following the removal of osteophytes should act as a surrogate of individual limb alignment. Although the overall limb alignment in this technique is independent of the initial plan the individual component position and joint line obliquity will vary depending on whether the knee was planned with a mechanical axis(mFA) or a kinematic axis(kFA) alignment. Assessment of the Perth Hip and Knee

Registry data would suggest on average a two degree difference in component position in both joint line obliquity and femoral rotation.

The need for soft tissue release to balance the knee in both MA and KA alignment makes them unsuitable for a computer enabled planning and balancing algorithm. This is due to variation in surgical skill and the difficulty in standardizing soft tissue releases. Functional Alignment is well suited to automated algorithms as the surgical steps to balance the knee (bony cuts) would be robot assisted and therefore have an in-built quality control. The development of computer algorithms to plan and balance the knee arthroplasty could potentially improve the overall quality of TKA performed.

Limits are placed in Functional alignment to prevent the severely arthritic knee with attenuated ligaments being placed in extremes of alignment. Understanding the “safe zone” for functional alignment is important for patient selection, implant choice, extent of intraoperative deformity correction, and long-term follow up. Furthermore, some disease pathology such as bone tumors, previous trauma, and congenital deformities may be present in conjunction with the arthritic knee and will have altered the native alignment of the limb. In such cases, using functional alignment to reproduce the altered anatomical alignment and mechanical function may have a detrimental effect on knee mechanics and wear.

A preliminary series by the principal investigator involved 122 TKR with mFA and over 350 kFA aligned knees since the introduction of RATKA into my practice. In an initial cohort of patients with functional alignment substantial differences were seen in femoral and tibial component position depending on whether a mechanical or kinematic plan was used. The final HKA angle was not changed as the coronal limb alignment is dictated by the collateral ligaments. The femur was 2 degrees valgus and the tibia 4 degrees varus with the kinematic plan compared to a neutral femur and 2 degree varus tibia with a mechanical plan. These small changes in position effect the three-dimensional relationships of the implants with the soft tissues. The initial cohort showed improved outcomes with the KA plan. There were confounding factors in that the groups were sequential, with MA plan group forming part of the surgeon’s learning curve. For the planned study a KA plan will be used as superior results have been seen in this group in the initial series..

1.1 Current evidence

There are no prospective studies looking at Functional alignment. Prospective studies comparing functional outcomes between the MA and KA groups have been performed but the main limitation of these studies has been the inability to accurately measure the desired deviation from neutral alignment as well as achieving the implant position to a high degree of accuracy. There is a paucity of studies using standardised techniques for intraoperative alignment and limited data relating these findings to clinical outcomes with long- term follow up.

Matsumoto et al (7) conducted a prospective randomised study on 60 patients with varus osteoarthritis undergoing computer navigated TKA and showed kinematic alignment was associated with improved postoperative angles of flexion, functional activity scores, and more parallel joint line orientation in relation to the floor during single- and double-leg standing compared to patients with TKA using mechanical alignment. The true mechanical axis, which runs from the centre of the femoral head to the inferior aspect of the calcaneus passed through a neutral position in the kinematic group and a slightly lateral position in the mechanical group. The authors suggested that this more natural weight-bearing position in TKA with kinematic alignment may reduce pre-existing concerns of increased polyethylene wear and implant loosening in this patient group. However, patient follow-up was limited to one year following surgery, two separate types of implants were used within each treatment group, patients with severe valgus/varus deformities were excluded, and intraoperative kinematic assessment was not performed despite the use of computer navigation.

Waterson et al (8) conducted a prospective randomised trial on 71 patients undergoing primary TKA and showed that there was no difference between kinematically aligned and mechanically aligned TKA with respect to the Knee injury and osteoarthritis outcome score (KOOS), American knee society score, 36-item short form survey (SF 36), European Quality of Life questionnaire with 5 dimensions for adults (EQ-5D), range of movement, two-minute walk, and timed up and go tests at one year following surgery. In this study, patient-specific cutting blocks were used to achieve kinematic alignment and standard extra- or intramedullary instrumentation was used to achieve mechanical alignment. No intraoperative navigation or robotic systems were used to confirm limb alignment, functional outcomes were only assessed for up to one year, and findings were poorly correlated to radiological outcomes.

Dossett et al (9) conducted a prospective randomised study on 88 patients and showed patients undergoing kinematic knee alignment had improved Oxford knee score (OKS), Western Ontario and McMaster Universities Arthritis Index (WOMAC), and improved range of motion compared to mechanically aligned TKA at a minimum of two-years follow-up. The odds ratio for having a pain-free knee was 3.2 with mechanical alignment compared to 4.9 with kinematic alignment in TKA. However, in this study accuracy of the cutting blocks was not assessed, preoperative scores were universally better in the kinematic alignment group compared to the mechanical alignment group, and the study was performed on private patients in the United States, which may have introduced a selection bias.

1.2 Need for a trial

There is a need for high quality evidence on the clinical and radiological benefits of functionally aligned TKA. This study would show if there is any superior outcomes to be obtained from functional alignment. Clinical and functional outcomes should also be correlated to longer-term outcomes to better establish the “safe zone” for functional alignment.

Currently the vast majority of TKA throughout the world is undertaken utilizing MA alignment. Any change to a newer technique from the current ‘gold standard’ would need to be justified by improved clinical outcomes as there is no long term longevity data for Functional Alignment. Both surgeons and patients are only able to consider the relative risks and benefits of this technique once they are defined by sound scientific evidence. This study will contribute to the body of this evidence.

2. Objectives

The overall aims of this prospective, randomised double-blinded controlled trial are to compare functional, clinical, and radiological outcomes in FA TKA versus MA TKA. Patients undergoing MA TKA will form the control group and those undergoing FA TKA will form the investigation group. A superiority design will be used to evaluate whether FA TKA provides superior outcomes compared to MA TKA. Primary and secondary objectives will be used to quantify and draw inferences on differences in the efficacy of treatment between the two groups. To ensure accuracy of planning and implantation robotic arm assisted surgery will be utilized in both groups (Stryker MAKO, Fort Lauderdale, FL). Standardised post-operative care will be undertaken to ensure the only difference between groups is alignment of implants.

2.1 Primary objective

- The primary objective of this study is to compare clinical outcomes at two years following surgery between FA TKA and MA TKA. The primary outcome measure for this study is the Forgotten Joint Score (FJS) at two years after surgery. The null hypothesis is that there is no difference in functional scores at two years following surgery between patients undergoing MA TKA (control group) versus FA TKA (investigation group). The hypothesis is that outcome measures obtained at two years after surgery in patients undergoing FA TKA are not achievable using MA TKA. Further PROMs will be used to further assess clinical outcomes including Forgotten Joint Score (FJS), Oxford Knee Score (OKS), Knee injury and osteoarthritis outcome Junior score (KOOS Jr), VAS Pain, and Kujala scores preoperatively and postoperatively at 3 months, 1 year and 2 years. Also health-related quality of life will be measured using European Quality of Life questionnaire with 5 dimensions for adults (EQ-5D-5L) preoperatively and postoperatively at 3 months, 1 year and 2 years. Range of movement (degrees) in knee joint during inpatient admission and postoperatively at 6 weeks, 3 months, 1 year and 2 years.

2.2 Secondary objectives The secondary objectives of the study are:

- Determine lower limb alignment achieved with both alignment techniques. Lower limb alignment as assessed using standing long leg x-rays performed postoperatively at 3 months. Measurements of the hip-knee-angle (HKA), medial proximal tibial angle (MPTA) and lateral distal femoral angle (LDFA). Also evidence of imbalance with implant lift off will be measured.

- Determine if there are any differences in analgesic requirements based on alignment method used. Analgesia requirements during inpatient admission and postoperatively at 6 weeks, 3 months, 1 year and 2 years will be measured.
- Determine whether alignment method utilized has an effect on the sagittal stability of the TKA. Assessment of sagittal stability at Preop, 3 months, 1 year and 2 years will be undertaken with an arthrometer “Lachmeter”.
- Determine whether alignment method utilized has an effect on functional outcomes. This will be assessed by a combination of
 - Maximum voluntary isometric force using a hand-held dynamometer at Preop, 3 months, 1 year and 2 years.
 - Sit to stand values as measure of function at Preop, 3 months, 1 year and 2 years.
- Intra-operative balance achieved with both alignment techniques. Surgeon blinded measurement of intraoperative balance achieved with Verasense sensor (smaller cohort)
- To determine if there is a difference in knee kinematics between the two techniques. Measurement of knee kinematics with Verasense sensor to assess presence or absence of medial pivot (smaller cohort)

3. Study Design

3.1 Study Type

This study is a prospective, single-centre, randomised, double-blinded, controlled study. Patients undergoing MA TKA will form the control group and those undergoing the FA TKA will form the investigation group.

3.4 Study population and groups

Patients with symptomatic knee osteoarthritis requiring TKA will be recruited from the [name] and [name] private rooms at Perth Hip & Knee Clinic. All patients will be screened for eligibility based on the predefined inclusion and exclusion criteria (section 5.1). Patients interested in participating in the study will be provided with an information leaflet and contact telephone number for further information (Appendix 19.7). Details of those patients expressing an interest to participate in the study will be recorded and then be forwarded to the Research Physiotherapist.

The Research Physiotherapist will telephone or meet with the patient to answer any additional queries and confirm whether or not the patient would like to participate in the study. More complex queries will be escalated to the Chief Investigator who will telephone the patient directly to discuss these issues further. Ideally, the time frame from the orthopaedic consultation to the decision to participate in the study will be approximately one week, which will give the patient sufficient time to perform further research, discuss study participation with family and/or friends, and contact the Research Physiotherapist for any additional information. This time frame may be shortened if a patient is agreeable with the study, due to patient flow and appointment availability at the consulting rooms. Contact details of the Research Physiotherapist and Chief Investigator are provided within the patient information leaflet.

If the patient agrees to participate in the study, the Orthopaedic fellow will randomise the patient into one of the two treatment groups. Patients allocated to mFA TKA will form the 'control group' whilst those allocated to kFA TKA will form the 'investigation group'. The method for randomisation is discussed in section 3.6. Written informed consent for both the operative procedure and inclusion into the study will be signed at the preadmission visit (Appendix 19.7). The procedure for obtaining written informed consent is discussed in more detail in section 5.

3.5 Sample Size In total, 100 patients will be enrolled in a 1:1 ratio between the two treatment groups. This will ensure that the minimum of 90 patients required to answer the study question are followed up for the duration of the study. The enrolment goal is to have at least 45 patients in each of the two treatment groups completing the study. Sample size calculation and statistical analysis are more comprehensively detailed in section 6.

3.6 Randomisation procedure

The system for randomisation will be the same throughout the study period and must be strictly adhered to. The following method will be used to allocate a trial patient to either the mFA TKA ('Control group') or to the kFA TKA ('Investigation group').

Randomisation will be carried out using a blocked effect. This method is designed to randomize subjects into two groups that result in equal sample sizes over time. The blocks will be small (n=4), and balanced within the predetermined group assignments, which will keep the number of subjects in each group similar at all times. There will be no stratification factors involved in the randomization as randomization will occur before the trial starts. Using a randomization website (www.random.org), a random number (between 1 and 100000) will be generated. This will form the "seed" number for the blocked randomization process. Using a randomization website (www.sealedenvelope.com) the randomization list will be created. Patients will be allocated in a sequential order of consent, strictly adhering to the allocation of groups. Screen shots of the randomization process and seed number will be taken throughout, and held from the CI to minimize randomization bias. The orthopedic fellow will then privately communicate to the CI the allocated group, to enable alignment and templating planning to be performed using the MAKO software. All patients and clinical staff recording the post operative clinical outcomes of interest will remain blinded to minimize performance and detection bias.

If the patient initially agrees to participate in the study and then changes his/her mind at a later stage, they are free to do so without any compromise to their further care. If this occurs before obtaining informed consent then the patient's decision will be relayed to the operating surgeon who will discuss suitable options directly with the patient, and organise postoperative follow-up care as per all routine (non-study) patients undergoing TKA at Perth Hip and Knee Clinic. There randomisation number will not be reallocated to the next patient, to ensure the blocks remain concealed. Drop in and out details are in section 6. If the patient agrees to participate in the study and then declines further inclusion after surgery has been performed, then the patient's follow-up care will be arranged as per routine TKA follow up at Perth Hip and Knee Clinic. Patients will be notified that once statistical analysis of the study has been performed, and all patient data has been de-identified for analysis, they will not be able to withdraw their clinical data. Statistical analysis of patients that drop out is discussed in section 6. Following randomisation and informed consent at the preadmission visit, baseline information will be recorded and documented in the Perth Hip and Knee Clinic Socrates database. Data handling and management are recorded in more detail in section 9.

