5.0 Consent

Patients with symptomatic knee osteoarthritis requiring TKA will be recruited from the private rooms at Perth Hip & Knee Clinic. All patients will be screened for eligibility based on the predefined inclusion and exclusion criteria (section 5.1) by a member of the clinical team. This includes the Orthopaedic Consultant Surgeon, Clinical Fellow, or Research Physio. If the patient meets the all of the inclusion criteria (section 5.1) and none of the exclusion criteria, and expresses an interest to participate in the study they will be provided with a patient information sheet (Appendix 19.7). This provides details about the study, treatment, follow-up and contact details for further information. All members of the clinical team are familiar with the study and will address any preliminary questions about the study. Details of those patients expressing an interest to participate in the study will be recorded in the patient contact sheet, which will be a password protected excel document that only [name], [name] and [name] will have access to.

One week after this outpatient consultation, the Research Physiotherapist will telephone the patient to answer any additional queries and confirm whether or not the patient would like to participate in the study. If the patient agrees to participate in the study, the Research Physiotherapist will randomise the patient into one of the two treatment groups. Patients allocated to mFA TKA will form the ‘control group’ whilst those allocated to kFA TKA will form the ‘investigation group’. The method for randomisation is discussed in Section 3.6. Written informed consent for both the operative procedure and inclusion into the study will be signed at the preadmission appointment.

The ideal length of time between initial consultation and obtaining informed consent for inclusion into the study is at least 1 week. This method provides time for potential participants to consider the trial and ask questions before written consent for participation is requested. This time may be shortened due to patient flow and clinic appointment availability, as long as the patient is agreeable. Consent will be taken by the study coordinator or by

a designated member of the surgical team who is familiar with the study.

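### A single stated block size of 4, with each allocation told to the CI, leaves the next allocation partly predictable: 33% certain at most on average, falling to 0% with two allocations pending

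*Combined protocol and SAP*

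**What the plan says.** Section 3.6 describes a permuted-block list made before the trial starts: "The blocks will be small (n=4), and balanced within the predetermined group assignments". There is one list, because "There will be no stratification factors involved in the randomization as randomization will occur before the trial starts", and the method does not change: "The system for randomisation will be the same throughout the study period and must be strictly adhered to". Section 3.5 sets the ratio and size: "In total, 100 patients will be enrolled in a 1:1 ratio between the two treatment groups". Patients take list positions in turn: "Patients will be allocated in a sequential order of consent, strictly adhering to the allocation of groups".

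On who knows what, section 3.6 keeps the seed and screenshots from the CI, but then: "The orthopedic fellow will then privately communicate to the CI the allocated group". A second safeguard is that the number of a patient who changes their mind before written consent is not reused, "to ensure the blocks remain concealed".

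On who meets patients before allocation, section 5.0 says of the screening team: "This includes the Orthopaedic Consultant Surgeon, Clinical Fellow, or Research Physio". Section 3.4 passes harder questions from undecided patients to the CI, who telephones them. Section 3.4 has the fellow randomising; section 5.0 has the research physiotherapist. Both place randomisation before written consent, which is signed at the preadmission visit. The documents do not say who holds the list, and describe no central service or sealed envelopes.

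**The concern.** Concealment requires that nobody who can influence a patient's entry can foresee that patient's arm. Hiding the list does not achieve this when the block size is fixed and known, there is one sequence to follow, and past allocations are disclosed: the rest of a block can be worked out by counting. The CI is documented as receiving each allocation and as having contact with patients before they decide.

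What is at stake is selection before randomisation. The plan records an expectation of benefit for the investigation arm (section 1 reports better results with the kinematic plan, and section 6.1 uses a one-tailed calculation on that basis). Entry also depends partly on judgement, such as the surgeon's agreement in section 5.1 that TKA is the most appropriate treatment. The primary outcome is patient-reported and there are 100 patients. If entry were influenced by a foreseen allocation, neither the intention-to-treat nor the per-protocol set would repair it.

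**Working it through.** The documents give no predictability figure, so there is none to reproduce.

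**Inputs.** Block size 4, unstratified, sequential (section 3.6); 1:1 and 100 patients, so 100/4 = 25 blocks (section 3.5); 10 recruits per month (section 4.1); about one week from consultation to decision, which may be shortened (sections 3.4 and 5.0). A 2:2 block has 6 equally likely orders. An allocation is certain when the known earlier ones in its block leave only one possible arm.

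**All earlier allocations known.**
- Certain: positions 1 and 2 never; position 3 when the first two match, probability 1/3; position 4 always. Expected share = (0 + 0 + 1/3 + 1)/4 = 33.3%, about 33 of 100. A single block gives 25% or 50%.
- Best guess (choose the under-represented arm): position 1, 1/2; position 2, 2/3; position 3, 1/3 × 1 + 2/3 × 1/2 = 2/3; position 4, 1. Average = (1/2 + 2/3 + 2/3 + 1)/4 = 70.8%, against 50% under full concealment.

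**Latest allocation still pending.** Only position 4 can be certain, when positions 1 and 2 match: (1/3)/4 = 8.3%. Best guess = (1/2 + 1/2 + 2/3 + 2/3)/4 = 58.3%.

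**Latest two pending.** None certain. Best guess = (1/2 + 1/2 + 1/2 + 2/3)/4 = 54.2%.

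**Which delay is realistic.** 10 per month × 12/52 = about 2.3 patients per week. Over a week between consultation and decision, two or so allocations could intervene. At first screening the lower figures are therefore more plausible; just before randomisation the higher ones are.

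**Unused numbers whose arm the CI never learns.** At an assumed 10% unfilled and no delay, among filled positions:
- Position 3 is certain with probability 0.9² × 1/3 = 0.270.
- Position 4 is certain with probability 0.9³ + 3 × 0.1 × 0.9² × 1/3 = 0.729 + 0.081 = 0.810.
- Share = (0.270 + 0.810)/4 = 27.0%. At assumed rates of 5% and 20% it is 30.1% and 21.3%.

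**Alternatives, all earlier allocations known.** The mixed rows come from simulating 1,500 lists of 100, with a guesser who knows the set of sizes but not where blocks end.

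| Scheme | Certain | Best guess right |
|---|---|---|
| Fixed 4 | 33.3% | 70.8% |
| Fixed 6 | 25.0% | 68.3% |
| Fixed 8 | 20.0% | 66.6% |
| Random 4 or 6 | 5.5% | 69.2% |
| Random 4, 6 or 8 | 2.2% | 67.9% |

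Random sizes nearly remove certainty but leave most of the guessing advantage.

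**The case against.** The strongest reply is that one third is a ceiling on the average. It needs every earlier allocation to be known at the moment the next patient is randomised, whereas choices about whom to approach are made at screening, roughly a week earlier. This stands, and it is why the result must be given as a range. It does not dispose of the point: the interval may be shortened, and the CI's calls to undecided patients come after the consultation, closer to randomisation.

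A reader might also infer that all the surgeons and other screeners know the sequence. The documents do not support that. Section 3.6 names only the CI as being told; other operating surgeons would know their own cases. Nor does the CI run the queue: the fellow or the physiotherapist allocates, in order of consent. A reader might infer that the block size was public during recruitment, or that patients could be turned away as too deformed. The documents show only that the size is stated in the protocol, and section 5.1 contains no deformity threshold.

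The rule against reusing numbers is a genuine safeguard and lowers predictability, but only where the CI does not learn the unused allocation, which the documents do not settle.

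Finally, it can be said that block size is the smaller gap: a list-holder who also screens could know every allocation whatever the blocks. That is fair as a possibility. The documents do not name the list-holder, so it cannot be asserted as fact, but the remedy must cover it.

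**Conclusion.** The point holds in bounded form. With a fixed, stated block of 4 and each allocation disclosed to the CI, withholding the seed and screenshots does not conceal the next allocation. The average share that is certain runs from 33% with no delay, through 8.3% with one allocation pending, to 0% with two; best-guess success runs from 70.8% through 58.3% to 54.2%. Unused numbers unknown to the CI reduce the no-delay figure, to about 27% at an assumed 10% unfilled.

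These figures assume that the CI knows the block size and can track position in the list. They measure opportunity. A reader might infer that a third of allocations were foreseen or that entry was steered; nothing in the documents shows either. This is a weakness that should be corrected for the remaining allocations, and not by itself evidence of bias.

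**What to change.** In section 3.6, for all allocations not yet made:

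1. Replace the fixed block of 4 with randomly varying sizes (for example 4, 6 and 8), recorded in a restricted file and not stated in the protocol.
2. Name a list-holder who takes no part in screening: an existing team member or an online service.
3. Release each allocation only after eligibility is confirmed and written consent is signed, and align sections 3.4 and 5.0 with that order.
4. Reconcile sections 3.4 and 5.0 on who randomises.

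Item 1 alone is not enough, because best-guess success would fall only from 70.8% to about 68%; items 2 and 3 address the rest.

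The cost is a short amendment and a new list for the unused positions, with no extra patients. The last block may be incomplete, leaving a final imbalance of at most 4 patients with a largest block of 8 (half the block). The change departs from the commitment to one system throughout, so it must be documented with its date. Allocation at the preadmission visit must also leave time for surgical planning; the documents do not give that interval.

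Nothing changes for patients already allocated. This version is dated 14/10/2021 and recruitment was planned from 03/2021; if the planned 10 per month had held for about seven months, some 70 of 100 positions would already be used. Actual accrual is not given.
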